## 5.0 STUDY DESIGN AND METHODS

### 5.1 Design/Study Type

Non-treatment intervention, randomized clinical trial of up to 350 participants [244 patient participants plus up to 106 of their caregivers as caregiver participants] (social behavioral research).

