### **Quality of Informed Consent:**

Understanding of chemotherapy benefits: The first primary outcome is a validated item from CANCORS. Patients are asked: “After talking with your doctors about chemotherapy, how likely did you think it was that chemo would cure your cancer?” Responses (“very likely,” “somewhat likely,” “a little likely,” “not at all likely,” “don’t know”) will be dichotomized to accurate (“not at all likely”) and inaccurate (all others). The pre-specified time-point for assessing the primary outcome is at the follow-up assessment, although patients will also be asked this question at baseline and the post-decision survey. Similar to CanCORS, patients will also be asked how likely they think it is that chemotherapy will “help you with problems or symptoms you are having because of your cancer,” “control the growth of your cancer,” and “help you live longer.” These additional items are included in the post-decision survey alone.

To assess understanding of treatment goal, patients are asked at the post-decision survey, “according to your doctor, what is the goal of the chemotherapy?” with the ability to choose any/all of the following response options: cure, control cancer growth, alleviate symptoms, prolong life, or other. Selecting either control cancer growth, and/or alleviate symptoms, and/or prolong life are defined as accurate understanding; “to cure” was inaccurate.

Understanding of chemotherapy risks: Modified items from Leighl et al will assess patients’ understanding of the potential risks (e.g. side effects) of their chemotherapy choice via participant questionnaire. These items include understanding of key risks (e.g., FOLFOX+/-bevacizumab (e.g. fatigue, nausea/vomiting and neuropathy), and FOLFIRI+/-bevacizumab (e.g. fatigue, nausea/vomiting, diarrhea, hair loss)). The accuracy of patients’ understanding of chemotherapy risks will be scored based upon the chemotherapy regimen they opted to receive, as described below:

- Patients initiating FOLFOX or FOLFOX bev will be considered to have an accurate understanding of risks if they respond that they are somewhat/very likely to experience neuropathy and nausea and a little/not very likely to experience hair loss  
We will create similar algorithms for all of the other chemotherapy regimens based upon well-established toxicity profiles.

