*Hypothesis:* Patients randomized to the intervention will be more likely to discuss their end-of-life care preferences with their healthcare proxy, and with their oncologist as compared to patients randomized to the usual IC process.

We will adhere to standard reporting principles delineated by the CONSORT statement for conduct and reporting of randomized trials. Primary reports will reflect the as randomized, "intention to treat" principle, however, we will also describe results according to actual exposure to the study interventions (based on patients' self-report of whether they reviewed the standard-of-care, or investigational chemotherapy informed consent materials). Fisher's exact test will test the difference between the study arms in the first primary outcome (the proportion of patients at follow-up assessment who fail to understand that chemotherapy is "not at all likely" to cure their cancer, as assessed by an item from CANCORS). We will also test the influence of the intervention on secondary outcomes (e.g. understanding of the goal of palliative chemotherapy, chemotherapy risks, decisional conflict,

**Title:** Improving Informed Consent for Palliative Chemotherapy: RCT of Usual IC versus Investigational IC

**Overall PI:** [name], Dana-Farber Cancer Institute

**Dana-Farber protocol version no./date:** v17 / August 30, 2017

achievement of preferred role in decision-making, satisfaction with chemotherapy IC process, prognostic understanding, advance care planning, discussion of end-of-life care preferences, satisfaction with MD communication, satisfaction with informed consent (IC) documents, decisional regret, emotional distress) using Fisher's exact or chi-square tests for dichotomous outcomes, and t-tests or Wilcoxon tests for linear outcomes. For missing data for primary or secondary outcomes, we will employ multiple imputation under a missing at random assumption.

Subset analyses will explore the effect of the intervention on 1) patients making a decision about 1st line treatment, 2) patients making a decision about 2nd line treatment, 3) patients with colorectal cancer, and 4) patients with pancreatic cancer.

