Because the effects of our intervention may be moderated by patient characteristics (e.g. age, race/ethnicity, health literacy and numeracy, communication preferences, decisional control preferences), we plan to conduct exploratory analyses investigating whether these factors moderate the effect of the intervention on outcomes including 1) accurate understanding of chemotherapy benefits, 2) satisfaction with communication and the IC tools, 3) decisional involvement, or 4) emotional distress. For example: we hypothesize that the IC tool may lead to decreased distress among patients who prefer a detail-oriented prognostic communication style, whereas it may lead to increased distress among patients who prefer a vague and support-focused prognostic communication style. We would also hypothesize that the effects of

**Title:** Improving Informed Consent for Palliative Chemotherapy: RCT of Usual IC versus Investigational IC

**Overall PI:** [name], Dana-Farber Cancer Institute

**Dana-Farber protocol version no./date:** v17 / August 30, 2017

the intervention may be greater among patients with higher health literacy scores. We will test these hypotheses using multivariable logistic or linear regression analyses (depending upon the dependent variable), including interaction terms for collinear factors, and controlling for potential confounding factors (e.g. age, race/ethnicity, marital status).

**Power:** In the CANCORS study, 80% of mCRC patients on 1st line chemotherapy thought that chemotherapy could potentially cure their disease (median of 4 months post-diagnosis). Based on previous series and projections about our patient mix, we anticipate that 60% of patients will have inaccurate expectations about the benefits of chemotherapy. If the intervention strategy is able to better align expectations with likely outcomes by one third (33%) we will deem the intervention as having major impact. If this benchmark 33% reduction is not achieved but the intervention exposed subjects nonetheless have expectations that are more accurate, we will view the intervention as beneficial but lacking major impact. Assuming a baseline 60% rate of inaccurate expectations about the benefits of chemotherapy, with a total of 194 patients, we will have 80% power to detect a 33% decrease (20% absolute decrease) in inaccurate expectations among patients exposed to the intervention with a one-sided type I error of 2.5%.

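### The stated 80% power at 194 patients matches a large-sample formula; Fisher's exact test, the named primary test, has 76.4%

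*Combined protocol and SAP*

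**What the plan says.** All inputs to the power claim are in the Power paragraph of Section 6.0. It begins "Assuming a baseline 60% rate of inaccurate expectations about the benefits of chemotherapy" and concludes that "with a total of 194 patients, we will have 80% power to detect a 33% decrease (20% absolute decrease) in inaccurate expectations", at a one-sided type I error of 2.5%. It names no test or formula.

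Earlier in Section 6.0 the primary test is named: Fisher's "exact test will test the difference between the study arms in the first primary outcome". Chi-square appears only as an alternative to Fisher's test for dichotomous secondary outcomes. Missing primary and secondary outcomes are to be multiply imputed under a missing-at-random assumption.

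Section 5.4, under Quality of Informed Consent, fixes the timing: "The pre-specified time-point for assessing the primary outcome is at the follow-up assessment". Section 4.0 sets 1:1 allocation. Section 5.1 gives the planned enrolment as "244 patient participants plus up to 106 of their caregivers as caregiver participants". No section says how 244 leads to 194.

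**The concern.** A power figure describes a particular test. With about 100 patients per arm and rates near 50%, Fisher's test rejects noticeably less often than the uncorrected chi-square test, so a sample size taken from the large-sample formula overstates Fisher's power. The number 194 is what that formula gives, which suggests that the size was computed for one test and the analysis written for another.

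This is the only power statement for the primary outcome. If it is wrong, the chance of missing the target effect is larger than stated, and a reader judging a null result would rely on the wrong figure. The sentence also leaves open whether 194 counts patients enrolled, randomised or observed at follow-up.

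**Working it through.** **Inputs**

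- Control rate p1 = 0.60 and intervention rate p2 = 0.40 (20-point absolute decrease): Section 6.0, Power.
- One-sided alpha 0.025 (z = 1.960) and power 80% (z = 0.8416): same paragraph.
- 194 patients at 1:1, so 97 per arm: Sections 6.0 and 4.0.
- Primary test, Fisher's exact: Section 6.0.

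**Step 1. Reproduce the plan's figure.** Pooled normal formula without continuity correction, with mean rate 0.50:

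n per arm = [1.960 × √(2 × 0.50 × 0.50) + 0.8416 × √(0.60 × 0.40 + 0.40 × 0.60)]² / 0.20²
= [1.960 × 0.7071 + 0.8416 × 0.6928]² / 0.04
= (1.3859 + 0.5831)² / 0.04 = 96.9

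Rounded up, this is 97 per arm, or 194 in total, and the formula's power at 97 per arm is 80.03%. The plan's figure is reproduced. The arcsine formula also gives 97 per arm (96.8). The continuity-corrected formula, which approximates Fisher's test, gives 106.7, i.e. 107 per arm or 214 in total.

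**Step 2. Exact power at 97 v 97.** Take every pair of counts (x, y) from 0 to 97, weight it by Binomial(97, 0.60) × Binomial(97, 0.40), and add the weights of the tables that are rejected. Fisher's test rejects when the one-sided hypergeometric p-value is at most 0.025; chi-square rejects when the pooled z is at least 1.960.

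| 97 v 97 | Fisher | Uncorrected chi-square |
|---|---|---|
| Power, 60% v 40% | 76.4% | 80.7% |
| Power, 60% v 40.2% (33% taken literally) | 75.5% | 79.9% |
| Maximum one-sided size (common rate near 50%) | 1.85% | 2.61% |

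The two-sided 5% version of Fisher's test also gives 76.4%. Slightly unequal arms (98/96 to 100/94) leave it between 76.4% and 76.5%.

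The gap is 80 − 76.4 = 3.6 points. Type II error is 23.6% against a stated 20%, which is 3.6/20 = 18% higher in relative terms.

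**Step 3. What would give Fisher's test 80%?** At 97 v 97 the intervention rate must fall to 39.15%, a drop of 20.85 points. At a 20-point drop, power by total analysed is:

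| Total analysed | Fisher power |
|---|---|
| 194 | 76.4% |
| 204 | 80.1% |
| 206 | 77.5% |
| 214 | 79.5% |
| 215 | 81.7% |
| 216 | 80.2% |
| 244 | 84.9% |

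The test is discrete, so power does not rise smoothly. It first touches 80% at 204 and drops back. Every total from 215 to 245 is at or above 80%.

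**Step 4. Dependence on the baseline.** With a one-third reduction, Fisher's power at 97 v 97 is 68.6% at a 55% baseline, 76.4% at 60% and 83.2% at 65%.

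**The case against.** The strongest reply is that the point is small beside the other uncertainties. Type I error is protected, sizing by a normal approximation is common, and moving the baseline from 55% to 65% changes Fisher's power by 83.2 − 68.6 = 14.6 points, about four times the gap. The plan itself cites 80% inaccurate expectations in an earlier colorectal series; at an 80% baseline and a 20-point drop, Fisher's test would have 83.4%. All this is true and limits the importance of the point. It does not make the sentence right, because the sentence is conditional on 60% and a 20-point drop.

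Second, the plan names no formula, so attributing 80% to the chi-square test is an inference from the match on 194. That is fair, and the arcsine formula fits too. Whichever large-sample formula was used, the named test falls short.

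Third, 244 patients are planned, and 215 is only 88% of 244. But the 80% is attached to 194. Under Section 4.0, patients enrolled during ongoing first-line treatment who make no new decision are never randomised, and a follow-up survey can be marked missing after three attempts. The documents give no rate for either, so 244 cannot be read as the analysed number.

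Fourth, missing outcomes are to be imputed, so 76.4% is the power of a complete-data Fisher test and not necessarily of the primary analysis as run. That stands as a qualification. Imputation cannot, however, raise the power of 194 randomised patients above what 194 complete outcomes would give.

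**Conclusion.** The power sentence is wrong as written for the test the plan names. With 97 v 97 observed outcomes, 60% v 40% and one-sided 2.5%, Fisher's exact test has 76.4% power, not 80%. This needs no input from outside the documents; it assumes an even split and complete outcomes. The attribution to an uncorrected large-sample formula is inferred from the exact match on 194.

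The consequence is modest. Validity, type I error, endpoints and decision rules are untouched. Whether the trial itself falls below 80% under its own assumptions depends on how many of the 244 reach the primary analysis, which the documents do not give.

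**What to change.** Restate the Power sentence, for example: *With 194 patients whose follow-up outcome is observed, Fisher's exact test has about 76% power at one-sided 2.5% to detect a fall from 60% to 40%.* Add a clause saying how 194 relates to the 244 patients in Section 5.1, with the allowance made for patients never randomised and for missing follow-up. If 194 is meant to count randomised patients with some outcomes imputed, say so.

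The cost is one sentence and a slightly less favourable figure. The restatement requires no change to enrolment, the analysis or data collection.

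Naming the uncorrected chi-square test as primary would also support the 80% (exact power 80.7%), but its one-sided size can reach about 2.6% when both true rates are near 50%. That trade is debatable and not needed to correct the plan.

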## 8.0 APPENDICES A-X

### **Study forms and assessments:**

- Appendix A: Checklist for Participating Sites
- Appendix B: Registration Form
- Appendix C: Patient Baseline Assessment
- Appendix D: Caregiver Baseline Assessment
- Appendix E: Patient Post-decision Assessment – Usual IC Arm
- Appendix F: Patient Post-decision Assessment – Investigational IC Arm
- Appendix G: Patient Follow-up Assessment – Usual IC Arm
- Appendix H: Caregiver Follow-up Assessment – Usual IC Arm
- Appendix I: Patient Follow-up Assessment – Investigational IC Arm
- Appendix J: Caregiver Follow-up Assessment – Investigational IC Arm
- Appendix K: Medical Record Abstraction Form
  
- Appendix L: Phone script for approaching potential participants via phone
- Appendix M: Phone script for assessment administration

### **Investigational IC Arm:**

- Appendix N: FOLFOX+/-bevacizumab booklet
- Appendix O: FOLFOX+/-bevacizumab video website
- Appendix P: FOLFIRI+/-bevacizumab booklet
- Appendix Q: FOLFIRI+/-bevacizumab video website
- Appendix R: FOLFIRINOX booklet
- Appendix S: FOLFIRINOX video website
- Appendix T: Gemcitabine + nab-paclitaxel booklet
- Appendix U: Gemcitabine + nab-paclitaxel video website
- Appendix V: Gemcitabine booklet
- Appendix W: Gemcitabine video website
  
- Appendix X: Global Medical Record Release Form
  
- Appendix Y: Study Letter for Caregiver Participants
